A (prospective/pilot) study evaluating the effect of cataract surgery on the daily activity levels of elderly patients.

[name], O.D.
[name].
[name], O.D., F.A.A.O.
[name].
[name], O.D., M.D.
[name], O.D.

Bennett and Bloom Eye Centers
[name]
[name]
[name]
[contact]
[contact]

Title: A (prospective/pilot) study evaluating the effect of cataract surgery on the daily activity levels of elderly patients.

Purpose: To evaluate the effect of bilateral cataract surgery with intraocular lens implantation on the daily activity levels of elderly patients.

Objective: The primary endpoint is the comparison of baseline activity levels to post-operative week two activity levels in patients undergoing bilateral cataract surgery using the ActiGraph GT9X wrist monitor.

Background: Cataract formation is a natural aging process that can be influenced by environmental factors such as exposure to ultra violet light and diet (1). Additionally, metabolic disorders, such as diabetes can lead to an earlier development of cataracts (2).

As cataracts develop, a patient's vision can be affected (3). Reduced vision can limit activities of daily living and may even reduce a patient's mobility (4). When this occurs, cataract surgery should be considered to help restore a patient's vision.

With the obesity and diabetic epidemic, proper diet and exercise is a major health initiative to control these diseases (5). If a patient's mobility is reduced as a result of poor vision - their ability to achieve adequate daily physical activity may also be effected (6). It is thought that improvement in vision may increase their activity levels and help combat these health issues.

This study will investigate the activity level of patients before and after undergoing cataract surgery to determine how improved vision quality from removal of the natural lens inside the eye and replacement with an artificial intraocular lens effects their activity level.

Study population: Adult patients undergoing bilateral cataract surgery and adult patients who have cataracts but are not undergoing cataract. Consecutive patients based on the inclusion criteria will be selected for the study.

Study design: Prospective

Masking: None

Randomization: None

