Method: Consecutive patients who meet the inclusion criteria will be asked to participate in the study. Patients scheduled for bilateral cataract surgery will be asked to wear a wrist accelerometer (Actigraph Inc, Pensacola, FL) 10 days prior to their cataract surgery in their first eye to determine their baseline activity level (7). The device is the size of a wrist watch and will have minimal burden to patients. Each monitor will be fitted

on the wrist and worn for 24 hours a day, but can be quickly removed for medical procedures, patient care, or hygiene needs. Data, such as steps per day, total movements per day, minutes being sedentary and minutes moving at various intensities (e.g. light, moderate and vigorous), will be collected and analyzed to determine a patient's overall general physical activity level. Set standards and cut offs will be used to correlate wrist accelerometry to physical activity and this has been studied previously. The patient will then undergo bilateral cataract surgery, having each eye done a week or two apart and both eyes set for distance. Cataract surgery will be performed in its usual manner using the standard post-operative care. Patients will then be asked to wear the wrist accelerometer again for 10 days following their surgery to measure their post-operative physical activity level. Wrist monitors can be mailed to and from patients using prepaid envelopes. The pre and post-operative data will be analyzed to determine cataract surgery's effect on pre and post-operative activity levels.

To control for placebo effects, a control group of patients who have visually significant cataracts but are not interested in cataract surgery at this time will also be asked to participate in the study. They will wear their wrist monitor for 10 days to collect base line data and then wear the wrist monitor again 14 days later for another 10 days.

Sample size: 30 patients will be enrolled in the study

Length of study: 12 months

Inclusion Criteria:

- Patients undergoing bilateral cataract extraction by phacoemulsification with intraocular lens implantation and a planned bilateral distance vision target or patients with bilateral cataracts who are not having cataract surgery
- Patients aged 60 years old or older
- Best corrected visual acuity worse than 20/20 in each eye (meaning 20/25 or worse)
- Non-comanged patients

Exclusion criteria:

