The risk of cataract surgery is not increased in this study and the routine cataract surgery procedure is not considered part of this study. With any surgical procedure there are risks and the standard risk of cataract surgery include infection, inflammation, loss of vision, increased intraocular pressure that may lead to glaucoma, bleeding, retinal detachment, damage to the cornea and corneal edema (swelling of the tissue in the front part of your eye), damage to the iris (the colored part of your eye), cystoid macular edema (swelling of the tissue in the back of your eye), or death, although this would be an extremely rare complication. You may need additional surgery to replace or reposition the intraocular lens or to treat any other ocular complications.

B. Potential benefits to be gained by the subject:

Potential increased physical activity and improvement in vision and activities of daily living would be a benefit to patients undergoing cataract surgery. Patients in both groups may benefit by knowing they are potentially contributing to the increasing body of scientific knowledge.

C. Potential benefits or information which may accrue to science or society in general, as a result of this work.

Evidence to determine if cataract surgery increases physical activity may help patients increase their exercise and combat obesity, diabetes, and heart disease.

D. Potential risks to subjects are reasonable in relation to anticipated benefits.

Cataract surgery is one of the most common surgeries performed in the United States and the risk of serious vision loss is low. Patients undergoing cataract surgery can expect to have an improvement in their vision. The risks from wearing a wrist watch size activity monitor are extremely low and pose a minimum burden to patients.

Monitoring/Reporting Adverse Events:

Adverse events will be monitored by the primary and sub-investigators at each study site. Adverse events will be documented and properly reported to the study IRB when

indicated. All investigators will have direct phone access to the lead investigator 24/7 for emergency situations. Data on adverse events will be reported and checked monthly by the primary investigator at each site as well as the lead investigator to ensure that there is no increased risk to the study subjects.

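### The non-surgery group is described as a control for placebo effects, but untreated, unmasked, self-selected patients cannot serve that purpose

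*Protocol*

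**What the plan says.** In the Protocol's Method section the non-surgery group is introduced with its purpose: "To control for placebo effects, a control group of patients who have visually significant cataracts but are not interested in cataract surgery" are to be invited. No other purpose is given for the group anywhere in the document.

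The rest of the design is stated plainly. The Masking entry is none, and the next entry reads "Randomization: None". Controls wear the monitor for a 10-day baseline and then "wear the wrist monitor again 14 days later for another 10 days". Under Examinations the non-surgery group has a baseline exam and nothing else. The surgery group has two operations and three post-operative exams.

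The Objective places the primary endpoint inside the surgery group: "The primary endpoint is the comparison of baseline activity levels to post-operative week two activity levels in patients undergoing bilateral cataract surgery". The Background goes further than the effect of surgery as such. It says the study will examine activity before and after surgery "to determine how improved vision quality from removal of the natural lens inside the eye" and its replacement with an artificial lens affects activity.

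**The concern.** A comparator controls for a placebo response only if it has that response too. The controls here have nothing done to them, know it, and joined the group by declining the operation. Nothing in the design would produce in them the expectation of benefit, or the response to repeated care contact, that may accompany surgery.

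What is at stake is interpretation. The Intended Use of Data section plans a journal paper. If that paper repeats that placebo effects were controlled, a reader could accept a rise in activity as the result of better vision, with expectation ruled out. The design gives no basis for ruling it out. An analysis plan could not repair this, because no analysis can subtract a response that the comparator never had.

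**Working it through.** There is no figure in the Protocol to reproduce. The check sets the stated purpose beside what each group undergoes.

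| Feature | Surgery group | Non-surgery group | Protocol source |
|---|---|---|---|
| How patients enter | Scheduled for bilateral surgery | Not interested in surgery at this time | Method |
| Procedure | Two operations | None; no sham described | Method, Examinations |
| Knowledge of treatment | Open | Open | Masking |
| Allocation | Not randomised | Not randomised | Randomization |
| Exams after baseline | Three | None listed | Examinations |
| Monitor periods | Two of 10 days | Two of 10 days | Method |
| Personal benefit named | "Potential increased physical activity and improvement in vision and activities of daily living would be a benefit to patients undergoing cataract surgery" | None; only the shared benefit: "Patients in both groups may benefit by knowing they are potentially contributing to the increasing body of scientific knowledge" | Risk/Safety Information, part B |

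The only row in which the groups are alike by design, and which bears on an observed change, is the monitor wear.

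Write the mean change in activity as a sum of parts:

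- V: effect of improved vision
- E: response to expecting benefit from surgery and to the care contact around it
- M: reactivity to wearing the monitor twice
- T: short-term change over time, which may depend on the type of patient

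Then:

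- Surgery group: change = V + E + M_s + T_s
- Non-surgery group: change = M_c + T_c
- Difference = V + E + (M_s − M_c) + (T_s − T_c)

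Three things follow.

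1. E remains in the difference beside V. One contrast cannot separate them. This is a consequence of the design and says nothing about how large E is.
2. The group can reduce the M and T terms, which is useful. The reduction is only partial, because self-selection gives no assurance that T_s equals T_c. The intervals between wear periods may also differ: controls have a stated interval, while surgery patients' timing depends on "having each eye done a week or two apart".
3. The primary endpoint uses the first line only. The control change does not enter it, so the wrong description does not alter that comparison.

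**The case against.** The best case for the Protocol is that *placebo effects* was meant loosely, as changed activity from wearing a monitor and being observed. Risk/Safety Information, part A, says routine cataract surgery is not considered part of the study. The monitor is then the main thing the study adds, and both groups wear it twice. On that reading the group does part of its job and only the term is wrong. The reading is possible, but the Protocol does not state it, and a reader of the planned paper would take the word in its ordinary sense. If it was the intention, the rewording below says so.

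A second objection stands in part. The Purpose, the Method and Risk/Safety Information, part C, speak of the effect of cataract surgery as a whole. For that question V and E need not be separated. The harm is therefore confined mainly to the Background's aim about vision quality.

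A third is that the limits are visible: masking and randomisation are openly declared absent, and this is a pilot of 30 patients. That lowers the risk of misleading a careful reader but does not make the sentence true. Nor does the accelerometer settle the matter. It limits reporting bias, but expectation can still change how much an unmasked patient actually moves. The benefit statements in part B are only weak support, since they do not show what controls expect.

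A reader might infer several stronger points that the document does not support:

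- *The primary analysis is wrong.* It is within the surgery group, and this Protocol specifies no between-group test.
- *A sham arm is required.* Lacking one is not an error; claiming placebo control without one is.
- *The monitor intervals are mismatched by a definite number of days.* The Protocol does not fix the starting points. The controls' 14 days could run from the end of the first wear or from its start, which would leave 14 − 10 = 4 days between periods. The surgery interval likewise depends on when the second wear begins. Under some readings the two intervals coincide, so one can say only that they may differ.
- *A known share of any observed change is placebo.* Nothing in the document gives the size of E.

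**Conclusion.** The point holds as a wrong design claim. The non-surgery group does not control for any expectation or care-contact response to surgery; at most it partly accounts for repeat monitor wear and short-term change over time. The consequence is for interpretation, chiefly attribution to improved vision. The primary within-group comparison and the broader question of the effect of having surgery are not overturned.

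The conclusion rests on taking *placebo effects* in its usual sense and on the Protocol's description of what controls undergo. It does not depend on sample size, on the wear intervals or on any assumed effect. No magnitude is claimed. The correction should be made, since the statement narrows wrongly what readers will think remains unexplained.

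**What to change.** In the Method section, replace the stated purpose of placebo control with:

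*To partly account for repeat monitor wear and short-term change over time*

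and add one sentence:

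*Because the groups are self-selected and unmasked and the control group has no procedure, any comparison of change between groups cannot separate the effect of improved vision from expectation or self-selection.*

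If the wear intervals are mentioned at all, say only that they may differ between groups. The change costs two sentences and leaves enrolment, procedures and the endpoint as they are. The downside is a more modest claim in the planned paper.
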